Using a randomized cross-over design, in the luteal phase of their menstrual cycles, PMDD women will receive either 1) one night of LWT (sleep 21:00-01:00 h, followed by wakefulness) plus 7 days of AM BWL (light-emitting diode-LED administered for 60 minutes, starting within 30 minutes of habitual wake time) or 2) EWT (wakefulness until 03:00 h, then sleep 03:00-07:00 h) plus 7 nights of PM BWL (administered 90 minutes before habitual sleep onset, for 60 minutes). Following this first intervention, patients will undergo one washout month with no intervention. The second intervention will be completed in the luteal phase of the following month and will be the treatment opposite the one previously performed. Total study duration, including evaluations and washout, will be 5 months (see Figure 1, Section 3, for detailed study flow diagram).

Sample Size and Population

In order to achieve the targeted enrollment goal of 40 completed subjects allowing for a 20% drop-out rate, 48 PMDD women ages 18-45 will be recruited to participate in the study.

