6.2.5 Washout

During washout Month 4, subjects will again perform the urine toxicology screening, Hamilton, BDI, BAI and PGWI ratings (once ***during the luteal phase, around the same time in the patient's cycle as the post treatment 2 ratings were collected***).

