9. STATISTICAL CONSIDERATIONS

9.1 General Design Issues

The design is a randomized cross-over contrasting LWT+AM bright light vs. EWT+PM bright light administered in the luteal phase of two separate menstrual cycles, and preceded by 2 evaluation months. To lessen the patient's burden, the 1-night EWT or LWT and the following 7-day BWL interventions will be conducted at home, given at a fixed point in each menstrual cycle, from day 1 to 7 after the mid-cycle LH surge. We anticipate that LWT+7 days of AM BWL (vs. EWT+PM BWL) will produce much greater mood benefits and larger physiological responses, than the one-time light pulses used in our earlier phase-shift studies.

The wake therapy and light interventions proposed in this application are based on our previous studies in PMDD and key published experiments by other investigators that indicate that the combined interventions are efficacious in other mood disorders after one week of treatment and maintained at 9-months follow-up. To provide optimal timing of interventions, we will administer wake therapy in the early-night vs. late-night and light pulses in the AM vs. PM at selected times in relation to sleep (within 30 min of waking and 90 min before sleep onset, respectively).

A crossover treatment design is employed to compare LWT+AM BWL vs. EWT+PM BWL responses within the same individual. As wake interventions lose effectiveness after 1 day, and light treatment effects after 3-4 days, we anticipate minimal carry-over effects of the wake plus light interventions administered a month apart. To further ensure no carry-over effects, there will be a month of no-intervention between the 1st and 2nd treatments. Because our previous studies clearly indicated differences between PMDD and NC subjects occurred primarily in the luteal menstrual cycle phase, we will treat during this menstrual cycle phase rather than in the follicular phase.

Hypothesis (H) 1: For PMDD patients in the luteal phase, LWT+AM BWL, compared with EWT+PM BWL, will A) Decrease scores on SIGH-SAD, BDI, BAI, and DMR, and increase global assessment of treatment effectiveness from baseline to post-intervention; B) Phase-advance urinary melatonin timing measures (acrophase, onset and offset time) in relation to clock time and to sleep measures (onset, end time and mid-sleep times); C) The magnitude of the phase-advance (B, above) will correlate with the magnitude of the symptom changes (A, above) by linear regression.

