9.2 Sample Size and Randomization

For our primary outcome measures of mood, based on our earlier data reflecting

seven days of light exposure alone² (i.e., without the ‘priming’ effect of wake therapy), we predict the following changes in mood in PMDD subjects (N = 40) after Late Wake Therapy plus AM Light vs. Early Wake Therapy plus PM Light: A significantly greater improvement (decrease in raw score) will be detected at the p = .05 level with (a) 71% power in Hamilton Rating Scale for Depression (HRSD) Score (Mean difference 3.15±9; effect size = .324); (b) > 99% power in atypical score (Mean difference 4.45±5; effect size = .78); (c) > 99 % power in Structured Interview Guide for the Hamilton Depression Rating Scale, Seasonal Affective Disorders (SIGH-SAD) Items (Mean difference 7.0±11; effect size = .627); (d) 86% power in Beck Depression Inventory (BDI) score (Mean difference 6.30±15; effect size = .378).

For the recovery criterion of $\geq 50\%$ decrease from baseline (Chi Square analyses): (a) 97% power for HRSD score (difference in proportions: .44); (b) 70% power for atypical score (difference in proportions: .30); (c) 86% for SIGH-SAD score (difference in proportions: .325); and (d) 93% power for BDI score (difference in proportions: .40). For the remission criterion of reduction to a score of ≤ 8 (Chi Square analyses): (a) 89% power for the SIGH-SAD score; (b) 44% power for the BDI score. All tests are two-tailed.

We also performed power analyses for the primary hypotheses, incorporating the longitudinal nature of the design for the proposed Random Regression model (also known as Multilevel Models, or Growth Curve Models). Procedures describes by Hedeker et al.⁶⁹ for Random Regression Models, with the above data, was used for the proposed study to estimated needed sample size. We assume a Type-I error level (alpha-level) of 0.05, drop-out rate of 10% to 15% and an autoregressive covariance structure, with correlation between sequential assessments set at 0.45 (based on our previous data). We are confident based on our results from these two separate approaches that the proposed study will have minimum power of 80% to yield a statistically significant result for a medium effect size. Here, medium effect size is defined as a treatment difference increasing linearly from 0 at baseline to .5 SD units at the last time point. Type 1 error will be controlled by correcting the p-value per domain.

Treatment Assignment Procedures

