response on the mood measures, the HRSD, SIGH-SAD and the BDI, is a decrease of > 50% in the pre-treatment/baseline score, while the remission criterion will be a decline to a value < 8 on the SIGH-SAD and BDI as per Terman et al.⁴¹ We will compare percentages of PMDD subjects achieving the Terman criteria in groups receiving different interventions using Chi Square analysis. Results from Expectation Forms and Horne-Ostberg Scales will be examined in relation to the magnitude of mood change after interventions as assessed by mood ratings, the Psychological General Well-Being Index (PGWI), and side effects checklists. We also will examine the effect of diagnosis and light intervention on measures of subjective sleep quality as measured by the Pittsburgh Sleep Quality Index (PSQI), and differences between groups or intervention on outcome measures as a function of the phase-angle difference (PAD) between melatonin timing (acrophase, onset, offset) and sleep (onset, end-time, mid-sleep) measures. Data for hypothesis 1.C will be analyzed similar to hypothesis 1.B. Data for hypothesis 2.A will be analyzed similar to hypothesis 1.A using RRM. Data from LWT + AM BWL, however, will be used only. Data for hypothesis 2.B will be analyzed similar to hypothesis 1.B by using individual slope in the correlational analysis. Data for hypothesis 3.A will be analyzed similar to hypothesis 1.B, and for hypothesis 3.B, similar to hypothesis 1.A using only EWT +PM BWL treatment data.

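### Response and remission in a within-woman crossover are to be compared by an unspecified Chi Square test, with no paired method named, and sections 9.2 and 9.6 differ on both cut-offs and on one response scale

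*Combined protocol and SAP*

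**What the plan says.** **Design.** The Précis says the second intervention "will be the treatment opposite the one previously performed". Section 9.1 states: "A crossover treatment design is employed to compare LWT+AM BWL vs. EWT+PM BWL responses within the same individual".

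**Analysis.** Section 9.6 assigns the random regression model to hypothesis 1.A and adds a count of responders. It compares the percentages of women meeting the "criteria in groups receiving different interventions using Chi Square analysis". No McNemar test, GEE, conditional or mixed logistic model, or other paired binary method appears in the document.

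**Power.** Section 9.2 also refers both binary criteria to Chi Square: "For the recovery criterion of $\geq 50\%$ decrease from baseline (Chi Square analyses") and "For the remission criterion of reduction to a score of ≤ 8 (Chi Square analyses"). Its response powers for N = 40, two-tailed at .05, are 97% (HRSD, difference .44), 70% (atypical score, .30), 86% (SIGH-SAD, .325) and 93% (BDI, .40). Its remission powers are 89% (SIGH-SAD) and 44% (BDI), with no proportions.

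**Definitions.** Section 9.6, which calls its definition operational, sets response at a fall of more than 50% on HRSD, SIGH-SAD and BDI, and remission at a value below 8 on SIGH-SAD and BDI.

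**The concern.** The groups named in section 9.6 are the same women measured twice. A chi-square test for independent groups computes the variance of the difference as if they were different women. With positive within-woman correlation that variance is too large: the test is conservative and gives back part of what the crossover was meant to gain. With negative correlation the error runs the other way. A paired test largely avoids this dependence.

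The endpoint itself is also loose. Two current sections classify a woman with a score of exactly 8, or a fall of exactly 50% (say 20 to 10), differently. One of them powers a response endpoint that the other does not define. Left open, the test, the cut-offs and the scale list could all be settled after the data are seen.

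**Working it through.** **1. The plan's own powers.** Section 9.2 gives differences but no base rates, so reproduction is conditional. For two independent groups of n = 40 with continuity correction:

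power = Φ[(d − 1/n − 1.96·se0) / se1], where se0 = √(2·p̄(1−p̄)/n) and se1 = √([p1(1−p1) + p2(1−p2)]/n).

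For the atypical score with assumed rates .65 and .35: se0 = √(2 × .25/40) = .1118 and se1 = √(.455/40) = .1067. The power is Φ[(.30 − .025 − .2191)/.1067] = Φ(.52) = 70%. Without the correction it is Φ[(.30 − .2191)/.1067] = Φ(.76) = 77.6%.

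When the lower rate is scanned over its whole range, the corrected two-sided version with 40 per arm can match all four response powers within 2 points. The lower rates needed are HRSD .10–.46, atypical .26–.44, SIGH-SAD .10–.14 or .54–.56, and BDI .18–.42. The uncorrected version at 40 per arm cannot match the atypical score (at least 77.6%) or BDI (at least 96.1%).

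Exact McNemar on 40 pairs, with lower rates of .20–.35 and a binary correlation of 0 to .2 assumed, gives 97–99%, 69–84%, 77–90% and 93–98% for HRSD, atypical, SIGH-SAD and BDI. Those ranges also contain the four stated figures. The powers therefore do not show which test was meant.

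**2. Size of an unpaired test on paired data.** Under no treatment effect the true variance of the difference is 2p(1−p)(1−φ)/n, where φ is the correlation of the two yes/no outcomes. The unpaired test uses 2p(1−p)/n. Its size is therefore about 2Φ(−1.96/√(1−φ)).

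The assumptions are a rate of 40% and a bivariate normal variable underlying the two outcomes with latent correlation r. At r = .45 the chance of responding in both periods is .2305, so φ = (.2305 − .16)/.24 = .29 and the size is about 2Φ(−2.33) = 2.0%. Exact enumeration of all paired tables (40 pairs, two-sided .05) gives:

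| r | Unpaired, uncorrected | Mid-p McNemar | Asymptotic McNemar |
|---|---|---|---|
| 0 | 5.2% | 4.6% | 5.2% |
| .20 | 3.8% | 4.7% | 5.0% |
| .45 | 2.1% | 4.5% | 4.5% |
| .50 | 1.8% | 4.4% | 4.4% |

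If the unpaired test were continuity-corrected, its size would be about 2.0% at .20 and 1.0% at .45.

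**3. Power for a .30 difference**, same enumeration (unpaired uncorrected / mid-p / asymptotic McNemar, %):

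| Assumed rates | r = 0 | r = .45 | r = .50 |
|---|---|---|---|
| 35% vs 65% | 79.5 / 75.2 / 77.6 | 83.2 / 88.4 / 88.7 | 83.7 / 89.8 / 90.0 |
| 25% vs 55% | 80.2 / 77.3 / 79.4 | 83.8 / 89.5 / 89.7 | 84.3 / 90.8 / 90.9 |
| 15% vs 45% | 85.2 / 83.9 / 84.8 | 88.6 / 92.8 / 92.9 | 89.0 / 93.8 / 93.8 |

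At r = .45 the unpaired test is 4.2 to 5.9 points behind, and at .50 it is 4.8 to 6.6 behind. At r = 0 it is ahead by 1.3 to 4.3 points (mid-p) or 0.4 to 1.9 points (asymptotic).

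**4. Which correlation is plausible.** Section 9.5.1 measures change in both treatment months from the single month 2 baseline. Take log scores B, P1 and P2 with equal variance σ² and equal pairwise correlation ρ (an assumption). Then Var(P1 − B) = 2σ²(1 − ρ) and Cov(P1 − B, P2 − B) = σ²(1 − ρ). The two changes correlate at .5 whatever ρ is. Values near .5 are thus plausible for response on that reading. Lower values may apply to remission, which is a threshold on the post-treatment score alone, or to response if the pre-treatment/baseline score of section 9.6 means each period's own pre-treatment rating.

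**5. Definitions side by side.**

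| | Section 9.2 | Section 9.6 |
|---|---|---|
| Response cut-off | at least 50% (called recovery) | more than 50% |
| Response scales | HRSD, atypical, SIGH-SAD, BDI | HRSD, SIGH-SAD, BDI |
| Remission cut-off | 8 or lower | below 8 |
| Remission scales | SIGH-SAD, BDI | SIGH-SAD, BDI |

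The documents give no score distributions, so the number of women on a boundary cannot be estimated.

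**The case against.** McNemar's test is a chi-square test, and a statistician running a crossover might well have meant it. This stands: the documents establish only that the form of the test is unstated. The word groups favours the unpaired reading but does not settle it. A reader might also infer from the reproduction in step 1 that section 9.2 counted 40 women as two independent groups of 40. The match is conditional on unstated rates, and exact McNemar can also reach the stated figures, so that inference is not supported.

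A reader might take the within-woman correlation from section 9.2, which assumes "an autoregressive covariance structure, with correlation between sequential assessments set at 0.45". That is a power assumption for the random regression model, and section 9.6 leaves that model's covariance to be chosen by AIC. Neither it nor its decay over successive ratings fixes the correlation between two binary outcomes in different cycles. The correlations above are illustrations only.

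The inequality signs may have been altered when the text was read from PDF: an underline lost from > or < would produce exactly this conflict. That possibility stands, and the source must be checked. It does not explain the scale difference, which rests on "b) 70% power for atypical score (difference in proportions: .30") in section 9.2. That difference is narrow: it is one response power for a score that section 9.5.1 treats as part of the SIGH-SAD, and the remission scales agree.

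**Conclusion.** The point holds as a minor one. The plan names no paired method for binary outcomes measured twice in the same woman. If the literal unpaired test were run, its size would depend on an unknown correlation: from about 5.2% at 0 to 1.8% at .50, for an assumed 40% rate and 40 complete pairs. The power given up for a .30 difference would be about 4 to 6 points at .45, slightly more at .50, and none near zero. As extracted, the two sections also disagree on both cut-offs, which affects only women exactly on a boundary, and on whether response covers the atypical score.

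Three stronger readings are not supported. The documents do not show that a wrong test was chosen, only that it is unspecified. False-positive inflation is not the likely consequence, because positive within-woman correlation makes the unpaired test conservative. The responder powers in section 9.2 are not shown to be wrong. The responder analysis is additional to the random regression model for hypothesis 1.A, which is unaffected.

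**What to change.** - In section 9.6, replace the Chi Square wording with a named paired method. One option is McNemar (asymptotic or mid-p) on women with both periods. The other is a GEE or mixed logistic model clustered on woman, with treatment and period as terms, which also keeps women with only one period.
- Check the inequality signs in the source, then use one response cut-off, one remission cut-off and one response scale list in both sections. State which rating is the baseline for response.
- In section 9.2, state which test the responder and remission powers refer to, with the assumed proportions.

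The cost is a few words in two sections, made before analysis, with no change to data collection or to the random regression model. The one statistical cost is the few points of power that McNemar loses if the within-woman correlation is near zero.

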10. DATA COLLECTION AND QUALITY ASSURANCE

10.1 Data Collection Forms

Data will be collected according to the schedule outlined in section 6.1. The blind clinical rater will collect all mood forms (Hamilton, BDI, BAI, PGWI, DMRs, SCID, etc.). All other forms (screening, consents, actigraphy, urine collection, side effects, urine toxicology, ovulation, etc.) will be collected by the study coordinator and/or research associate, who are not blind to the study condition. Forms will not contain any patient identifiers; only patient numbers corresponding to each participant in accordance to the confidentiality protocols stipulated in section 11.3 below.

10.2 Data Management

The data monitor will review all data collection forms on an ongoing basis for completeness and accuracy as well as compliance with study protocol. She will enter patient data into a central database, which will be verified against the original source document by independent lab personnel. The quality assurance officer will oversee the completeness and accuracy of this central database prior to proceeding with statistical analyses.

Data forms for this study are as follows:

- Menstrual Assessment Questionnaire to collect patient's menstrual, medical and psychiatric history during screening,
- Hamilton: The Hamilton Rating Scale for Depression (HRSD)⁵⁶ (as a validated objective, interview-based assessment of depression). Atypical depression symptoms as part of the Structured Interview Guide for the Hamilton Depression Rating Scale, Seasonal Affective Disorders version (SIGH-SAD)⁶⁰ (as atypical symptoms in particular respond to light treatment⁶¹) Mania⁶² ratings (to document any clinical induction of manic symptoms by the wake or light interventions),

- Beck Depression Inventory (BDI)⁵⁷ (as a validated subjective assessment of depression),
- Beck Anxiety Inventory (BAI)⁵⁸ (as a subjective assessment of anxiety symptoms)⁶³,
- The Psychological General Well-Being Index (PGWI)⁶⁴ (as a subjective assessment of general well-being),
- Daily Mood Ratings (DMR)⁵⁴ (as a subjective 100 mm visual analogue scale that include core PMDD symptoms of anxiety and irritability),
- Expectation form measuring patient expectation for change with the interventions (100 mm line from “much worse” to “much better”),
- Horne-Östberg subjective scales to assess morningness and eveningness⁶⁵,
- Seasonal Pattern Assessment Questionnaire (SPAQ)⁶⁶ to subjectively assess seasonality,
- Pittsburgh Sleep Quality Index (PSQI)⁶⁷ to assess subjective sleep quality,
- Sleep Quality Ratings⁶⁸ (a 100 mm visual analogue scale to assess subjective sleep quality),
- Structured Clinical Interview for DSM-IV (SCID)^{51, 52} (a detailed objective questionnaire to establish diagnosis),
- Actiwatch Log to record subjective sleep times (bed time, wake time, naps, etc.) and assist in editing and analyzing objective sleep data,
- Urine Collection Log to record time and total urination volume associated with each collected urine sample and necessary for post-assay data analysis,
- Side- Effects Checklist to record potential side effects from treatment. Forms will be used to assess treatment safety,
- Global Assessment of Treatment Effectiveness (subjective assessment).

10.3 Quality Assurance

10.3.1 Training

Laboratory staff members are well experienced in the collection, processing and analysis of all protocol-related data. Nevertheless, as technologies and procedures continue to evolve, the quality assurance officer and study coordinator will ensure that all necessary training in the areas of data collection, processing, analysis, and reporting; are routinely performed via specialized training courses offered at the University of California, San Diego.

10.3.2 Quality Control Committee

In accordance with the Data and Safety Monitoring Plan, laboratory personnel will provide yearly study reports to the Independent Monitoring Committee (see section 7.6 for list of committee members) to evaluate data quality, ensure protocol goals are met and recommend any necessary modification to protocol.

10.3.3 Metrics

The Quality Assurance Officer (QAO) will train personnel and implement data collection procedures and practices to ensure maximum consistency, reliability and validity of data acquisition, data entry and data analysis. Immediately after input to computer data files, the QAO will check the data file against the original data source(s) (e.g., paper records) and will examine means and standard deviations of data inputs for outliers, normality/skewness, etc.

A key element in the data acquisition process will be the routine use of check lists and spread sheets which identify individual components, as well as the person(s) responsible for executing each component of the research protocol. The QAO and Clinical Coordinator will examine check lists daily to verify that strict compliance with procedures is achieved.

Mood Measures:

To establish a reliable diagnosis of PMDD, an experienced, Ph.D.-level clinical rater will administer and interpret mood measures over two consecutive menstrual cycles. In consultation with the Principal Investigator, a licensed psychiatrist, diagnoses of PMDD will be established based on DSM-IV criteria. After they are admitted for study, the clinical rater will evaluate patients according to the evaluation schedule outlined in section 6.1 using standard clinical rating instruments, including HRSD, BDI, BAI, etc. before and after treatment (sleep + light). Mood improvement will be determined based on differences between before and after measures. Further, the exit interview will provide an opportunity for the patient express satisfaction with the protocol and to identify issues or problems in data collection, thereby providing valuable feedback for improving procedures. Complaints from participants regarding aspects of the protocol that are too burdensome will be evaluated and alterations considered.

Urine Melatonin:

The Clinical Coordinator will instruct each patient and demonstrate procedures for completing the Urine Log and collecting, transferring urine samples to tubes (using urine kits provided to them prior to cycle day 10 in months 2, 3 and 5) and freezing samples at home. The Research Associate will telephone patients to prompt them to collect samples when menstruation approaches (based on menstruation histories), will collect frozen urine kits and data logs within 3 days of collection (but not before completion of actigraphy measures), catalogue identifying information, and store samples at -70⁰ centigrade. On the day the patient transfers samples to the laboratory, missing samples or log entries will be noted and the participant will be instructed on the importance of providing complete samples and records. As urine collections (particularly during mornings) may be problematic for women in school or work, patients that cannot collect some morning/evening urine samples are instructed to record time of missed collections in order to later extrapolate 6-SMT excretion rates before proceeding with analysis. Patients that are completely unable to collect urine will not be excluded from participation in the study as they will still collect mood, activity, light and sleep data for analysis of treatment outcomes.

Sleep Measures:

The Clinical Coordinator will instruct each patient on the proper use of the Actiwatch device and the completion of its accompanying log. Actigraphy devices and logs will be collected by the research associate at the same time as the urine samples. Data will be verified against logs to ensure completeness and accuracy, as well as to monitor compliance with sleep and light protocols. Compliance with wake therapy will be monitored by means of half-hourly message left to a laboratory voice mail. Timing of these messages must correspond to the required treatment time. Failure to comply with wake therapy will result in repetition of wake therapy prior to commencing light treatment.

As precise timing of ovulation is essential to the protocol, Recruitment Officer/Clinic Coordinator will train personnel to read luteinizing hormone (Clearblue®) indicators. The Coordinator and another staff member will independently examine the Clearblue® on the day after the participant phones in with her putative ovulation identification. If both agree that ovulation has occurred, the participant will be advanced to the next phase of testing. If not, further testing will be postponed until clear-cut evidence of ovulation is obtained.

